16.6.4. Safety

ECG Parameters
RR Interval
 If RR interval (msec) is not provided directly, then RR can be derived as: (1/HR)/1000(i.e. 1 / heart rate where the heart rate is taken as part of the ECG) If ECGs are manually read, the RR value preceding the measurement QT interval should be a collected value THEN do not derive.
Corrected QT Intervals
 When not entered directly in the eCRF, corrected QT intervals by Bazett's (QTcB) and Fredericia's (QTcF) formulas will be calculated, in msec, depending on the availability of other measurements. QTcF or QTcB values entered by the site will always be presented in output. IF RR interval (msec) is provided (or can be derived from HR) then missing QTcB and/or QTcF will be derived as:

$$QTcB = \frac{QT}{\sqrt{\frac{RR}{1000}}}$$

$$QTcF = \frac{QT}{\sqrt[3]{\frac{RR}{1000}}}$$

201247 | Statistical Analysis Plan RAP Amendment 3 Final_V1 21 Aug 2020 | TMF-2068612 | 1.0

CONFIDENTIAL

201247

Laboratory Parameters
 If a laboratory value which is expected to have a numeric value for summary purposes, has a non-detectable level reported in the database, where the numeric value is missing, but typically a character value starting with '<x' '="" or="">x' (or indicated as less than x or greater than x in the comment field) is present, the number of decimal places in the observed values will be used to determine how much to add or subtract in order to impute the corresponding numeric value. Example 1: 2 decimal places: '< x' becomes x – 0.01 Example 2: 1 decimal places: '> x' becomes x + 0.1 Example 3: 0 decimal places: '< x' becomes x – 1 </x'>
Reticulocyte Production Index (RPI) will be calculated, by GSK S&P, as:
RPI = Reticulocyte Count [%] x [Hematocrit [%] / 45] x 1/RMT
To use the formula above Hematocrit and Reticulocyte Count must be converted from the SI unit (proportion) to a percentage by multiplying by 100 (note that the GSK code describes reticulocyte count as a percentage even though it is a proportion). Where Normal Hematocrit [%] = 45 and RMT (reticulocyte maturation time) is found from the table
below:
Haematocrit RMT
>=40% 1.0
30% to 39.9% 1.5
20% to 29.9% 2.0
<20% 2.5
 Corrected calcium will be calculated, by GSK S&P as: Corrected Calcium [mmol/L] = Serum Calcium [mmol/L] + 0.02 * (40[g/L] – Serum Albumin[g/L]) Where Normal Serum Albumin = 40 [g/L]
 eGFR (estimated Glomerular Filtration Rate) will be calculated by GSK S&P at all timepoints, this will also be provided directly by the vendor at screening. The GSK calculated value at screening will be used as primary for reporting (e.g. will be used as baseline if appropriate). The calculation will be as follows:

SI Results MDRD (GFR) (ml/min/1.73 m^2) = (175 * (PD9S3/88.4) -1.154) * (Age -0.203 * Race * Sex) Where PD9S3 = Serum Creatinine (UMOL/L), Race = 1.212 for Black & 1.000 for other, Sex = 1.00 for males and 0.742 for females.

16.6.5. Pharmacodynamic

Derived Parameters for Serum Level of OSM

% Target Engagement (TE%)

TE (%) = 100*(1- [Free OSM/Baseline Free OSM]) Note: predicted value will be presented, this will be derived by CPMS

201247

16.6.6. Biomarkers

Derived Parameters for Fibrosis and Histology
ELF
The ELF test will be provided by the vendors using on the ADVIA Centaur system. For reference, here is the formula as specified in the laboratory manual (Rev. C, 2015-01).
The ELF score can be calculated manually or by the ADVIA Centaur systems. For detailed information about how the system calculates results, refer to the system operating instructions.
Note The auto-calculation feature is only available for the ADVIA Centaur XPT system, for the ADVIA Centaur XP system software version 7.0 or higher, and for the ADVIA Centaur CP system software version 6.0 or higher. For the ADVIA Centaur system, and earlier versions of the ADVIA Centaur XP and ADVIA Centaur CP systems, calculate the ELF score manually.
To calculate the ELF score manually for the ADVIA Centaur and ADVIA Centaur XP systems, first obtain results for the ADVIA Centaur HA, PIIINP, and TIMP-1 assays, and then use the following equation to calculate the ELF score:
ELF score = $2.278 + 0.851 \ln(C_{HA}) + 0.751 \ln(C_{PIIINP}) + 0.394 \ln(C_{TIMP-1})$
Concentrations (C) of each of the constituents are in ng/mL.
To calculate the ELF score manually for the ADVIA Centaur CP system, first obtain results for the HA, PIIINP, and TIMP-1 assays on the ADVIA Centaur CP system, and then use the following equation to calculate the ELF score:
ELF score = $2.494 + 0.846 \ln(C_{HA}) + 0.735 \ln(C_{PIIINP}) + 0.391 \ln(C_{TIMP-1})$
Concentrations (C) of each of the constituents are in ng/mL.
Note The ELF score is a unitless numerical value.
Alaba SMA
αSMA= αSMA Area (μm²)/(Dermis Area).
2GSSc Skin Biomarker
2GSSc = -27.6844 + (4.46*(Baseline THBS1)) + (5.31*∆MS4A4A) + (4.96*∆THBS1)
Where, Δ MS4A4A and Δ THBS1 are change from baselines and Baseline THBS1 is baseline value of THBS1 on log 2 scale
General
If biomarker values are below the lower limit of quanitification, data will be imputed as half the lower limit of quantification (LLQ).

If biomarkers are above the upper limit of quantification, data will be imputed as for lab data, where the number of decimal places in the observed values will be used to determine how much to add in order to impute the corresponding numeric value:

- Example 1: 2 decimal places: '> x' becomes x + 0.01
- Example 2: 1 decimal places: '> x' becomes x + 0.1
- Example 3: 0 decimal places: '> x' becomes x + 1

201247

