5.3.1. Derivations and Handling of Missing Baseline Data

Definition	Reporting Details
Change from Baseline	= Post-Dose Visit – Baseline
% Change from Baseline	= 100 x [(Post-Dose Visit – Baseline) / Baseline]
Ratio to baseline	= Post-Dose Visit / Baseline
Nadir	= Lowest post-baseline value of endpoint for a participant ^[1]
Days to Nadir	= Study Day of Nadir – 1 ^[1]
Maximum Change from Baseline	 Calculate the change from baseline at each given timepoint and determine the maximum absolute change
Minimum value at timepoint	= The lowest value of the parameter in the reported group at the specified timepoint.

NOTES:

- 1: When there are multiple instances of the lowest value then the nadir used for reporting will be the earliest occurrence of that value.
- Unless otherwise specified, the baseline definitions specified in Section 5.3 Baseline Definitions will be used for derivations for endpoints / parameters and indicated on summaries and listings.
- Unless otherwise stated, if baseline data is missing no derivation will be performed and will be set to missing.
- The baseline definition will be footnoted on all absolute summary and change from baseline plots. 'Note: Baseline
 is defined as the pre-dose Day 1 assessment, unless unavailable, in which case it is the latest pre-dose
 assessment.'
- If there are multiple measurements (i.e. ECG) the derivation will be based on the average values where available.

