13.1.2. Summary Measure

Interim 2:

The baseline values will be summarised without treatment groups using the safety population presenting summary statistics assuming a skewed distribution for the systemic markers. A scatter plot of the raw baseline values will be presented alongside the geometric mean \pm standard error.

The Spearman's and Pearson's correlations of the baseline values transformed using log base 10, will be calculated and presented for each combination of endpoints. The correlations will also be presented as scatter plots for each pair of endpoints. Where both the correlations are >-0.3 and <0.3 the correlation will be suppressed from the outputs.

Final analysis

Standard summaries at each planned timepoint will be used for biomarker endpoints assuming a skewed distribution. The ratio of the post-baseline to baseline values and fold change (geometric ratio <1 then fold change is -1/geometric ratio otherwise fold change is geometric ratio) will also be summarised.

Systemic biomarkers will be summarised and presented using a log 10 scale while the histology and gene sets will be summarised and presented using a log 2 scale. 2GSSc skin biomarker and GSVA Scores will be summarised and presented on linear scale.

Line plots of the unadjusted geometric means \pm standard error for log transformed data and unadjusted means \pm standard error for linear data will be presented by treatment group at each visit. Individual participant plots of the raw values will be presented by treatment group and individual plot lines are differentiated by MMF use at Day 1 (solid

201247

line denote subjects on mycophenolate at day 1 and dashed line denote subjects not in mycophenolate at day 1). Information on positive autoantibodies is added to the subject ids in the legend as per Section 6.1.

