13.1.5. Statistical Analyses / Methods

Details of the planned displays are provided in Appendix 12 and will be based on GSK Data Standards and statistical principles.

The endpoints / variables defined in Section 13.1.1 will be summarised using descriptive statistics, graphically presented (where appropriate) and listed.

Longitudinal model

The ratio to baseline for the following systemic biomarkers will be analysed using a Bayesian MMRM analysis using the log transformed data including only the placebo and GSK2330811 300mg arms:

- Pro-C3
- Pro-C6
- PINP
- ELF
- COMP
- PIIINP
- IL-6
- MCP-1 (Rename MCP-1 as CCL2 for displays)
- CCL-18

Non-informative priors will be used in these analyses, specifically the prior for the regression coefficient will be normally distributed with mean 0 and a variance of 10^6 . The variance-covariance matrix for the within subject error across the visits will use an inverse-Wishart prior distribution, consisting of the identity matrix and the degrees of freedom will be the number of visits included in the model.

The models will be adjusted for the following covariates: MMF use at day 1, baseline value, treatment, visit, treatment by visit and baseline by visit interactions.

201247

The change from baseline within each treatment group and the difference in the change from baseline across the treatment groups (GSK2330811 300mg – placebo) will be calculated and are back transformed to give the ratio to baseline and the ratio of the change relative to placebo respectively.

Posterior medians and equal tailed 95% credible intervals will be presented. In addition, the probability the ratios are <1 and fold changes (Posterior Medians, as ratio < 1 then fold change is -1/ratio otherwise fold change is ratio) will also be calculated. The line plot of the adjusted posterior medians \pm credible intervals at each visit will be presented.

ANCOVA

The ratio to baseline of log transformed and change from baseline of linear data for the following skin histology and gene expression mRNA sequencing endpoints will be analysed using a Bayesian ANCOVA analysis including only the placebo and GSK2330811 300mg arms:

- Alpha SMA (Excluding Insufficient samples)
- COMP
- CCL2
- 2GSSc
- Disease Signatures GSVA Scores (Upregulated and Downregulated)
- Lung Fibrosis Signature GSVA Score
- Cell Modular Signatures GSVA Scores (Fibrosis, M1-Macrophage and M2-Macrophage)

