Non-informative priors will be used in these analyses, specifically the prior for the regression coefficient will be normally distributed with mean 0 and a variance of 10^6 . The prior for the variance parameter will be an inverse-gamma (shape=0.001, scale=0.001).

The models will be adjusted for the following covariates: MMF use at day 1, baseline value and treatment.

Nature of Data	Output Presentation
Log Transformation	 The change from baseline and difference in the treatment groups (GSK2330811 300mg – placebo) will be back transformed to give ratio to baseline and ratio of the change relative to placebo respectively. Posterior medians, equal tailed 95% credible intervals, probability that ratios < 1 and fold change (i.e., Posterior Medians, as ratio < 1 then fold change is -1/ratio otherwise fold change is ratio) will be presented.
Linear	 Change from baseline and the difference in the treatment groups (GSK2330811 300mg – placebo) will be calculated. Posterior medians and equal tailed 95% credible intervals will be presented. Except for Downregulated GSVA score, the probability that difference < 0 will be calculated. For Downregulated GSVA score, the probability > 0 will be calculated.
201247

The plot of the adjusted posterior medians \pm credible intervals along with individual ratio to baseline or change from baseline values based on the endpoints will be presented.

Joint model

In addition to the Bayesian MMRM analysis, the ratio to baseline or change from baseline based on the endpoints for the following four key biomarkers will be modelled using a multivariate Bayesian analysis including only the placebo and GSK2330811 300mg arms:

- Alpha SMA (Excluding Insufficient samples)
- CCL2 gene assessed from the skin sample through RNA sequencing
- PIIINP assessed from the serum sample
- 2GSSc

Non-informative priors will be used for all parameters. The variance-covariance matrix for the within subject error across the endpoints will use an inverse-Wishart prior distribution consisting of the identity matrix and 4 degrees of freedom.

The model will be adjusted for endpoint (allows each endpoint to have their own intercept), treatment by endpoint interaction term, MMF use at day 1 by endpoint interaction, and baseline by endpoint interaction term. If the model does not converge, the covariate for MMF use will be removed from the model.

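### The baseline covariate in the 2GSSc ANCOVA is a rescaled THBS1, so baseline MS4A4A goes unadjusted: no systematic bias, but some exposure to chance imbalance that is cheap to remove

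*SAP*

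**What the plan says.** SAP Section 16.6.6 gives the score. It opens "2GSSc = -27.6844 + (4.46*(Baseline THBS1", closes the brackets, and adds 5.31 times the MS4A4A delta and 4.96 times the THBS1 delta. The note below the formula reads "THBS1 are change from baselines and Baseline THBS1 is baseline value of THBS1 on log 2 scale". Section 5.3.1 defines change from baseline as "Post-Dose Visit – Baseline".

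Section 13.1.2 says "2GSSc skin biomarker and GSVA Scores will be summarised and presented on linear scale". In Section 13.1.5 the ANCOVA outcome is "The ratio to baseline of log transformed and change from baseline of linear data", and 2GSSc is on the ANCOVA list, so the analysed quantity is the change in 2GSSc. The covariates are then stated: "The models will be adjusted for the following covariates: MMF use at day 1, baseline value and treatment".

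2GSSc also enters the joint model, where "four key biomarkers will be modelled using a multivariate Bayesian analysis". That model includes "MMF use at day 1 by endpoint interaction, and baseline by endpoint interaction term".

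MS4A4A is one of the individual genes of interest in Section 13.1.1.3.1. It is not on the ANCOVA list or the joint-model list as an endpoint, and neither model names its baseline as a covariate. The SAP does not say in words what baseline 2GSSc consists of.

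**The concern.** Adjusting a change score for its own baseline absorbs regression to the mean: participants who start high tend to fall, and the covariate removes the part of the arm difference that arises because one arm started higher. This works when the baseline covariate measures what is changing. For 2GSSc it does so for only one of the two genes. Two participants with the same THBS1 and very different MS4A4A at Day 1 have the same baseline score, yet their expected changes in MS4A4A, and so in 2GSSc, differ.

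With about 5 placebo participants, a chance difference between arms in baseline MS4A4A is likely to be appreciable, and it passes into the 2GSSc treatment difference. The SAP reports the posterior probability that this difference is below zero. Suppose baseline MS4A4A happens to be higher in the active arm. A larger fall would then be expected there without any drug effect, and that probability would be pushed up.

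**Working it through.** The documents state no precision or sample-size figure for 2GSSc, so there is none to reproduce. For the group sizes, Protocol Section 10.1 uses 15 active and 5 placebo for log(PIIINP). Its half-width reproduces: 0.521 × sqrt(1/15 + 1/5) × t(0.975, 18 df) = 0.565, as stated.

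**Baseline score.** Setting both deltas to zero gives baseline 2GSSc = -27.6844 + 4.46 × baseline THBS1. With THBS1 = 8, this is -27.6844 + 35.68 = 7.9956, whether baseline MS4A4A is 3 or 9.

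**Change score.** Subtracting the baseline score gives change in 2GSSc = 5.31 × change in MS4A4A + 4.96 × change in THBS1.

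**Weight of MS4A4A in the change.** By coefficient it is 5.31/(5.31 + 4.96) = 51.7%. If the two changes had equal SDs and were independent, its variance share would be 5.31²/(5.31² + 4.96²) = 53.4%. The documents give no SDs. If the ratio of change SDs (MS4A4A to THBS1) runs from 0.5 to 2 and the correlation of the changes from 0 to 0.5, the share runs from 22% to 82%.

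**Effect of an ordinary imbalance.** Assume log2 SD 1 for each gene, genes uncorrelated at baseline, 15 v 5, and baseline to Day 85 correlation rho. The SD of the arm difference in baseline MS4A4A is sqrt(1/15 + 1/5) = 0.516. A 1-SD imbalance moves the treatment difference by 5.31 × (1 - rho) × 0.516:

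- rho 0.3: 5.31 × 0.7 × 0.516 = 1.92
- rho 0.5: 5.31 × 0.5 × 0.516 = 1.37
- rho 0.7: 5.31 × 0.3 × 0.516 = 0.82

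Against the SD of the estimate without the MS4A4A term (4.10, 3.66 and 2.85 in the table below), these are 0.47, 0.37 and 0.29 SDs.

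**Effect of adding the covariate.** There were 4,000 simulated trials per setting, with 15 v 5, no true effect and MMF use in both models. Least squares stood in for the vague-prior Bayesian fit. The two columns give the SD of the treatment estimate.

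| rho | Correlation between genes | Baseline 2GSSc only | Plus baseline MS4A4A | Change in SD |
|---|---|---|---|---|
| 0.3 | 0 | 4.10 | 3.74 | -9% |
| 0.3 | 0.5 | 4.94 | 4.76 | -4% |
| 0.3 | 0.8 | 5.11 | 5.13 | 0% |
| 0.5 | 0 | 3.66 | 3.48 | -5% |
| 0.5 | 0.5 | 4.33 | 4.29 | -1% |
| 0.5 | 0.8 | 4.61 | 4.72 | +2% |
| 0.7 | 0 | 2.85 | 2.80 | -2% |
| 0.7 | 0.5 | 3.46 | 3.49 | +1% |
| 0.7 | 0.8 | 3.74 | 3.84 | +3% |

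The mean estimate was close to zero under both models in every setting. Counting the cohort 1 placebo participant (15 v 6), the reductions with uncorrelated genes are similar: 8%, 5% and 1%.

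**The case against.** The strongest reply is that nothing is wrong on average. Allocation is randomised, so the estimate is unbiased with or without the term, and chance imbalance is ordinary sampling error that the 95% credible interval already carries. This stands. A reader might infer from the algebra that the planned estimate is biased; the documents do not support that.

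A second tempting inference is that baseline MS4A4A drives about half of the change score. It does not follow. The 51.7% is the coefficient share of the change in MS4A4A. How much of that change its baseline level explains depends on a correlation that is not given.

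Third, if the genes correlate at r at baseline, the THBS1 covariate already does part of the work. The expected shift from a given MS4A4A imbalance shrinks by a factor of about 1 - r², for example by 16% at r = 0.4. SAP Section 16.13.1 lists both genes as upregulated in SSc skin, which hints at positive correlation within patients but does not prove it. At high correlation the extra term gains nothing or costs a little. Keeping a model for about 20 participants small is a defensible preference, and Section 13.1.5.1 already plans to drop covariates if a model fails to converge.

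Fourth, Tables 8.9 and 8.10 and Figures 8.10 and 8.12 show MS4A4A by treatment, so an imbalance could be seen. Section 5.5.1 also leaves room for further covariates. That allowance is unspecific, however, and invoking it for MS4A4A once an imbalance has been seen would be a post hoc choice. It does not replace naming the covariate now.

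Finally, 2GSSc is exploratory, no formal hypothesis is tested (Protocol Section 3.1), and no decision threshold is stated for it.

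**Conclusion.** The point holds as a limited one. By the SAP's own formula, the baseline covariate in the 2GSSc ANCOVA adjusts for baseline THBS1 only, while the gene with the larger coefficient in the change has no baseline adjustment. The SAP does not tell the reader this. The consequence is exposure to chance imbalance and a modest loss of precision, not systematic error. Adding the covariate changes the SD of the estimate by about -9% at best (rho 0.3, genes uncorrelated) and about +3% at worst (rho 0.7, genes correlated at 0.8).

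These sizes rest on assumed equal log2 SDs, 15 v 5-6 participants and assumed correlations. A common SD other than 1 would rescale the shifts in score units but not the percentages; unequal SDs would change both.

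A reader might conclude that the joint model needs the same repair. It shares the feature, but it is built with one baseline and one missing-baseline sub-model per endpoint, so a second baseline for one endpoint is not a simple addition, and the gain shown here does not justify restructuring it. Severity is low: this is a cheap improvement to an exploratory analysis.

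**What to change.** In the SAP Section 13.1.5 ANCOVA, for 2GSSc only, add baseline log2 MS4A4A alongside the existing baseline 2GSSc covariate, which is equivalent to baseline THBS1. In Section 16.6.6, state that baseline 2GSSc reflects THBS1 only.

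Leave the joint model as it is. If the term is wanted there, add it only as a sensitivity analysis with its own specification for a missing MS4A4A baseline.

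The cost is a sentence or two of SAP text and one more coefficient in a model with about 20 participants, which could slightly reduce precision if the two genes are strongly correlated. No new data are needed, because MS4A4A is already measured in the Day 1 biopsy.

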16.7. Appendix 7: Reporting Standards for Missing Data

16.7.1. Premature Withdrawals

Element	Reporting Detail
General	 Participant study completion (i.e. as specified in the protocol) was defined as completion of all assessments on Day 197(Week 28).
	 In cohort 1 non-evaluable participants will be replaced.
	 In cohort 2 withdrawn participants are not replaced in the study.
	• All available data from participants who were withdrawn from the study will be listed and all available planned data will be included in summary tables and Figures, unless otherwise specified.

16.7.2. Handling of Missing Data

Element	Reporting Detail
General	 Missing data occurs when any requested data is not provided, leading to blank fields on the collection instrument: These data will be indicated by the use of a "blank" in participant listing
	displays. Unless all data for a specific visit are missing in which case the data is excluded from the table.
	 Answers such as "Not applicable" and "Not evaluable" are not considered to be missing data and should be displayed as reported.
Outliers	• Any subjects excluded from the summaries and/or statistical analyses will be documented along with the reason for exclusion in the clinical study report.

16.7.2.1. Handling of Missing and Partial Dates

Element	Reporting Detail
General	 Partial dates will be displayed as captured in subject listing displays.
Adverse Events	 The eCRF allows for the possibility of partial dates (i.e., only month and year) to be recorded for AE start and end dates; that is, the day of the month may be missing. In such a case, the following conventions will be applied for calculating the time to onset and the duration of the event: Missing Start Day: First of the month will be used unless this is before the start date of study treatment; in this case the study treatment start date will be used and hence the event is considered On-treatment as per Appendix 4. Missing Stop Day: Last day of the month will be used. Completely missing start or end dates will remain missing, with no imputation applied. Consequently, time to onset and duration of such events will be missing.
Concomitant Medications/ Medical History	 Partial dates for any concomitant medications recorded in the CRF will be imputed using the following convention: If the partial date is a start date, a '01' will be used for the day and 'Jan' will be used for the month If the partial date is a stop date, a '28/29/30/31' will be used for the day (dependent

201247

Element	Reporting Detail
	on the month and year) and 'Dec' will be used for the month.
	The recorded partial date will be displayed in listings.

